5.1.2 Hypotheses and Statistical Methods for Secondary Objectives

5.1.2.1 Secondary Immunogenicity Hypotheses

No hypotheses were tested.

5.1.2.2 Statistical Methods for Secondary Immunogenicity Objectives

For descriptive purposes, the statistics presented on [Table 5.1](#) will be produced.

Immunogenicity analyses will be performed in those BL collected before receiving an authorized/approved COVID-19 vaccine. Immunogenicity data after receiving an authorized/approved COVID-19 vaccine will be listed separately.

5.1.2.3 Secondary Efficacy Hypotheses

No hypotheses were tested.

5.1.2.4 Statistical Methods for Secondary Efficacy Objectives

The efficacy profile of the study vaccine candidate will be investigated with collected COVID-19 cases of efficacy endpoints including virologically-confirmed COVID-19-like illness and serologically-confirmed SARS-CoV-2 infection. Efficacy analyses will be performed on COVID-19 cases collected before receiving an authorized/approved COVID-19 vaccine. COVID-19 cases before, on and after receiving an authorized/approved COVID-19 vaccine will be listed. As the vaccine formulation used in VAT00001 is no longer investigated further and the number of COVID-19 cases collected before receiving an authorized/approved COVID-19 vaccine would be limited, planned efficacy analyses might not be performed for the final analysis.

Correlates of risk

To evaluate the correlate of risk of the collected COVID-19 cases including virologically-confirmed COVID-19-like illness and serologically-confirmed SARS-CoV-2 infection, logistic regression models will be conducted to investigate the relationship of COVID-19 cases defined above and immunogenicity responses measured by neutralization assay and ELISA. In addition, Other explanatory/independent variables under consideration are intervention groups ([vaccine, placebo]; [low-dose, high-dose, placebo]). Separate models will be performed for different consideration of intervention groups. The log10 value of neutralizing antibody titers at D36 for cohort 2 and D21 for cohort 1 are the main immunogenicity responses for this analysis. In case the majority of participants have below LLOQ neutralizing antibody titers in the placebo group, the value of below LLOQ will be treated as ½ LLOQ. Alternatively, the antibody titers of immunogenicity responses will be categorized as a discrete variable by quantile. Dose-response curve will be modeled based on the analyses in a Bayesian manner.

Vaccine efficacy

Vaccine efficacy (VE) will be assessed with the collected COVID-19 cases. The VE will be estimated as follows:

$$VE = 1 - \frac{C_v/N_v}{C_p/N_p}$$

where

- C_v and C_p are the numbers of COVID-19 cases meeting the considered secondary endpoint definition in the vaccine and placebo groups, respectively;
- N_v and N_p are the numbers of subjects in the vaccine and placebo groups, respectively.

The aggregated vaccine groups will be used for VE assessment include 1) pooled all vaccine arms; 2) pooled low-dose and high-dose with adjuvants arms; 3) pooled high dose with adjuvants arms; 4) pooled cohort 1 vaccine arms and cohort 2 vaccine arms.

The statistical methodology will be based on the use of the two-sided CI of VE. The CIs for VEs will be calculated by an exact method assuming a binomial distribution of the number of cases in vaccine group conditional on the total number of cases:

Let $q = \frac{C_V}{C_V + C_P}$, the proportion of cases belonging to vaccine group among the total number of cases. Given the total number of cases, C_V has a binomial distribution $(q, C_V + C_P)$. Thus, a CI for q may be constructed using the exact Clopper-Pearson method for binomial proportions.

As $\frac{q}{1-q} = \frac{C_V}{C_P}$, the VE estimate given above may be restated as follows:

$$VE = 1 - \frac{C_V/N_V}{C_P/N_P} = 1 - \frac{N_P}{N_V} \times \frac{q}{1-q}, \text{ which is a strictly decreasing function of } q.$$

Finally, CI of the VE will be constructed based on the CI of q .

Bayesian inference will be performed on VE to assessed the conditional probability $\text{Prob}(VE > VE_0) > 95\%$ | observed number of COVID-19 cases), where VE_0 is a threshold from 0% and 30%, through the posterior distribution of q . Non-informative uniform beta(1, 1) prior will be used.

Analyses can be performed for pooled vaccine groups as specified above.

For descriptive purposes, the statistics presented on [Table 5.1](#) will be produced.

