This is a parallel group prevention study, stratified into 2 age groups based on age at enrollment: the younger adult age group (18-49 years) will be randomly assigned to one of 11 arms; the older adult age group (≥ 50 years) will be randomly assigned to one of 10 arms. Participants, outcome assessors, Investigators, laboratory personnel, and the majority of sponsor study staff (except those involved in the ESDR and for concerned participants only) will be blinded to vaccine assignment group (formulation and adjuvant); injection schedule will be unblinded; and those preparing/administering the study interventions will be unblinded to vaccine group assignment.

Number of Participants:

Approximately 440 participants 18 years of age and older (300 adults 18 through 49 years of age and 140 adults 50 years of age and older) are planned to be randomized.

As a precautionary step, a Sentinel Safety Cohort of 6 participants (younger adults only) within each dosing group from Cohort 1 will be enrolled. An ESDR will be performed, including evaluation of safety data and laboratory measures to D09 in Cohort 1 among younger adults 18-49 years of age. Upon acceptable safety demonstrated from unblinded data review by limited members of the Sponsor Study Team (Responsible Medical Officer [RMO], Study Biostatistician and Programmer, Pharmacovigilance Science Expert, and Global Safety Officer), the remaining participants in Cohort 1 and all participants in Cohort 2 will be enrolled.

Intervention Groups and Duration:

A total of 440 participants are planned to be enrolled as shown below:

Participants 18-49 years of age					
Cohort	Group	Dose Level*	Adjuvant	N	
				Sentinel Safety† (N=30)	Total (N=300)
Cohort 1: 1 injection	1	5 μ g	AF03	6	20
	2	5 μ g	AS03	6	20
	3	15 μ g	AF03	6	20
	4	15 μ g	AS03	6	20
	5	Placebo	None	6	20
Cohort 2: 2 injections	6	5 μ g	AF03	N/A	20
	7	5 μ g	AS03	N/A	60
	8	15 μ g	AF03	N/A	20
	9	15 μ g	AS03	N/A	60
	10	15 μ g	None	N/A	20
	11	Placebo	None	N/A	20

Participants 50 years of age and older				
Cohort	Group	Dose Level*	Adjuvant	N (N=140)
Cohort 1: 1 injection	1	5 µg	AF03	10
	2	5 µg	AS03	10
	3	15 µg	AF03	10
	4	15 µg	AS03	10
	5	Placebo	None	10
Cohort 2: 2 injections	6	5 µg	AF03	10
	7	5 µg	AS03	30
	8	15 µg	AF03	10
	9	15 µg	AS03	30
	10	15 µg	None	N/A‡
	11	Placebo	None	10

*Antigen Formulation naming for each dose level: CoV2 preS dTM antigen: Formulation 1 (low-dose [5 µg]); Formulation 2 (high-dose [15 µg])

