The study will be conducted in adults 18 years of age and older. Clinical and epidemiological data from the COVID-19 pandemic have consistently indicated a higher risk of severe complications and death in older adults (35) (36). Therefore, it is considered of great relevance to generate data in the older adult population to inform schedule and formulation selection that will serve the general adult population, including those at particular risk of poor outcomes. A Sentinel Safety Cohort among younger adults is included to provide preliminary short-term safety data prior to enrollment of older adult participants. The study incorporates several measures to mitigate the theoretical risk of vaccine-associated ERD. These include a higher representation of the younger adult strata for the same reason, given that adults over 50 years of age have also been overrepresented in studies describing critical illness and death, although to a lesser degree than those older than 75 years (35). Therefore, the proposed design aims at generating data that will allow selection of the relevant formulations and injection schedule accounting for potential age

effects. Data for each formulation will be generated in both younger adults and older adults, allowing the evaluation of the consistency in the patterns of immune response for each formulation between the 2 age strata; additionally, aggregated “main” effects by age will be evaluable by comparing pooled older adult data (n=120 across vaccine formulations) and pooled younger adult data (n=240 across vaccine formulations with corresponding data in the older strata).

Evidence to date indicates that individuals with chronic medical conditions are at increased risk of severe outcomes associated with COVID-19 (37). The exclusion of individuals with chronic underlying conditions is considered an additional risk mitigation measure to address the theoretical phenomenon of immune enhancement. Clinical and epidemiological data indicates that the overrepresentation of older adults among those with critical or fatal COVID-19 illness is meaningfully ameliorated when stratified/controlled for the presence of chronic medical conditions (26). Exclusion of individuals with chronic medical conditions from this trial mitigates the potential (theoretical) risk of exacerbating the occurrence of critical or fatal outcomes as a result of study participation.

Rationale for Active Arms

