6.3 Measures to Minimize Bias: Randomization and Blinding

6.3.1 Randomization and Allocation Procedures

On the day of enrollment, participants who meet the eligibility criteria and sign the Informed Consent Form (ICF) will be stratified by 2 age groups (18-49 years and ≥ 50 years) and then be randomly assigned to receive 1 injection (Cohort 1) or 2 injections (Cohort 2) of CoV2 preS DTM investigational study vaccine or placebo. As shown in [Table 4.2](#), within each cohort:

- participants aged 18-49 years:
 - will be randomized to 6 groups to receive Antigen Formulation 1 (low-dose [5 μ g]) with either AF03 or AS03 adjuvant; Formulation 2 (high-dose [15 μ g]) with either AF03, AS03, or no adjuvant; or placebo (Note: unadjuvanted arm included in Cohort 2 only)
 - N = 20 participants in each group, except for AS03-adjuvanted groups in Cohort 2 with 60 participants in each group
- participants aged ≥ 50 years:
 - will be randomized to 5 groups to receive Antigen Formulation 1 (low-dose [5 μ g]) or Formulation 2 (high-dose [15 μ g]) each with either AF03 or AS03; or placebo
 - N = 10 participants in each group, except for AS03-adjuvanted groups in Cohort 2 with 30 participants in each group

The study will initially enroll 30 participants (6 within each dosing group from Cohort 1) 18-49 years of age, who will comprise the Sentinel Safety Cohort. Participants in this cohort will receive 1 injection of study intervention to which they were randomized, and safety and laboratory parameters up to D09 will be evaluated. Upon demonstration of acceptable safety, the remaining participants in Cohort 1 and all participants in Cohort 2 will be enrolled and randomized.

A subset of 87 participants in Cohort 2 (60 participants 18-49 years of age [18 per group in AS03-adjuvanted vaccines; 6 per group in all other study groups]) and 27 participants ≥ 50 years of age [9 per group in AS03-adjuvanted groups; 3 per group in all other study groups, with the exception of the unadjuvanted group for which there will be no older adults]), will be randomly assigned to a cellular-mediated immune (CMI) subset.

Site staff will connect to the Interactive Response Technology (IRT), enter the identification, security information, and confirm a minimal amount of data in response to IRT prompts. The IRT will then provide the group assignment and have the site staff confirm it. The full detailed

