Additionally, to evaluate independent determinants of primary immunogenicity endpoints, regression models may be constructed for GMT titers and occurrence of 4-fold rise in serum neutralization titer relative to D01 at D22 for cohort 1 and D36 for cohort 2. When the outcome/dependent variable is a continuous numerical variable, linear models may be utilized; when the outcome/dependent variable is a categorical variable, logistic regression models may be utilized. Explanatory/independent variables inserted in these models would include age group (18-49 years, ≥ 50 years), antigen dose level (low-dose, high-dose), and adjuvant (none, AS03, AF03). Models evaluating antibody titers or rates at D22 for cohort 1 and D36 for cohort 2 as the outcome variable would include also an explanatory variable corresponding to the injection schedule (1-injection, 2-injections). Multiplicative interaction terms will be included in expanded models to assess for evidence of effect modification. Non-significant interaction terms with critical value < 0.05 can be removed from the models.

For descriptive purposes, the statistics presented on [Table 5.1](#) will be produced.

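### The correlate-of-risk models do not list age group as a covariate, so the titre odds ratio may be confounded by age

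*SAP*

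**What the plan says.** Protocol 9.4.3.2 leaves the correlates method to the SAP, so SAP 5.1.2.4 is the only specification. There, "logistic regression models will be conducted to investigate the relationship of COVID-19 cases defined above and immunogenicity responses measured by neutralization assay and ELISA". The main exposure is stated as follows: "The log10 value of neutralizing antibody titers at D36 for cohort 2 and D21 for cohort 1 are the main immunogenicity responses for this analysis". The section also allows titre in quantile categories and a Bayesian dose-response curve.

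On covariates it says: "Other explanatory/independent variables under consideration are intervention groups ([vaccine, placebo]; [low-dose, high-dose, placebo". The list stops there, and a separate model is fitted for each grouping. Age group does not appear, and no correlate analysis by age is planned.

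Elsewhere age is treated as a design and analysis factor:

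- Protocol 6.3.1: participants "will be stratified by 2 age groups" before random assignment.
- SAP 5.1.1.4, immunogenicity regressions: "Explanatory/independent variables inserted in these models would include age group".
- Protocol 4.2: the design is meant to support formulation and schedule selection "accounting for potential age" effects, "allowing the evaluation of the consistency in the patterns of immune response for each formulation between the 2 age strata".

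**The concern.** Randomization protects comparisons between arms. It does not protect a comparison between people with high and low titres, because titre is a response to vaccination. Within any arm, whatever drives both titre and the chance of becoming a case is mixed into the titre coefficient. Age is the obvious candidate, since the plan itself stratifies on it and models it for immune response.

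The second efficacy objective is the association between antibody response and risk, and Protocol Table 3.1 lists correlates of risk or protection as the endpoint. If older participants respond less and also differ in risk, part of the age difference is attributed to titre. The titre association is overstated if older participants are at higher risk and understated if they are at lower risk. Intervention group in the model would not remove this, as the check below shows.

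**Working it through.** **Plan's own figures.** The documents give no case count, odds ratio or power for this analysis. The relevant figure they do give is the pooled adjuvanted-vaccine N by age, 240 and 120 (Protocol 9.2). From Protocol Table 4.2, groups 1-4 and 6-9:

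- Younger: 20 + 20 + 20 + 20 + 20 + 60 + 20 + 60 = 240.
- Older: 10 + 10 + 10 + 10 + 10 + 30 + 10 + 30 = 120.

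Both reproduce.

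**Can intervention group stand in for age?** Share aged 50 and over by category:

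| Category | Older / total | Share |
|---|---|---|
| Placebo | 20 / 60 | 33.3% |
| Low dose | 60 / 180 | 33.3% |
| High dose, including the younger-only unadjuvanted arm | 60 / 200 | 30.0% |
| All vaccine arms | 120 / 380 | 31.6% |

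Age is nearly balanced across categories. Any confounding therefore acts within category, through individual titres, and intervention group cannot absorb it.

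**Size if age is left out.** Let p be the older share, d the older-minus-younger difference in log10 titre, SD the titre spread within age group, and OR_age the age odds ratio for being a case. Approximately:

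shift in log OR = ln(OR_age) × d × p(1−p) / [SD² + d² × p(1−p)]

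Only p = 120/360 comes from the documents, giving p(1−p) = 0.222. The other inputs are assumptions: SD 0.5, d = −0.3 (2-fold) or −0.5 (3.2-fold), OR_age 0.5 or 2, and no true titre effect.

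- d = −0.3: 0.693 × 0.3 × 0.222 / (0.25 + 0.02) = 0.171, so the odds ratio per log10 becomes 1.19 (OR_age 0.5) or 0.84 (OR_age 2).
- d = −0.5: 0.693 × 0.5 × 0.222 / (0.25 + 0.056) = 0.252, giving 1.29 or 0.78.

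A logistic simulation with 2,000,000 vaccinees per scenario and 6% baseline risk gives slightly different values:

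| d | OR_age 0.5 | OR_age 2 |
|---|---|---|
| −0.3 | 1.16 | 0.83 |
| −0.5 | 1.25 | 0.76 |

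With age in the model, the null odds ratio returns to 0.995-1.001. With a true odds ratio of 0.60, omitting age gives 0.45 to 0.77.

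A second simulation used the planned arm proportions, with dose category in the model and a true odds ratio of 0.5. It gives 0.39 to 0.64 without age when both links are present, and 0.49 to 0.51 with age. If either link is absent (d = 0 or OR_age = 1), leaving age out makes no difference.

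**Sensitivity to titre spread.** The vaccine category pools both schedules, both adjuvants and the unadjuvanted arm, so the spread may exceed 0.5. With SD 0.7 the null odds ratios are 1.09 and 0.91 (d = −0.3), and 1.14 and 0.87 (d = −0.5).

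**Comparison with sampling error.** Assume 360 vaccinees and 6% risk, about 22 cases. The standard error of the log odds ratio is about 1/√[360 × 0.06 × 0.94 × (SD² + d² × 0.222)]. For SD 0.5 that is 1/√(20.3 × 0.27) = 0.43 at d = −0.3 and 1/√(20.3 × 0.306) = 0.40 at d = −0.5. A 95% interval then spans a factor of exp(1.96 × 0.40) = 2.2 to exp(1.96 × 0.43) = 2.3 either way. The simulated shifts run from ln(1.16) = 0.15 to |ln(0.76)| = 0.27 on the log scale, or roughly 0.35 to 0.7 of a standard error.

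**The case against.** The strongest reply is that the second link is not in the documents. Protocol 4.2 ties older age to severe complications and death. The modelled outcomes are any virologically confirmed illness or serologic infection. The same section says the excess of older adults among critical or fatal cases shrinks once chronic conditions are accounted for, and those conditions are excluded here (E13). Long-term-care residents (E17) and staff caring directly for COVID-19 patients (E18) are excluded too. The effect of age on titre is described only as potential, with no size. This stands. A reader might infer that the titre odds ratio is confounded; the documents support only that it may be.

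A reader might also infer that the models firmly adjust for intervention group, or that the plan tests age effects. Neither is so. Intervention group is only a candidate covariate, and Protocol 9.1 states that nothing is tested, so the age main effect is a descriptive summary.

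A further reply is that the objective is an association, and an unadjusted association is a legitimate descriptive answer, particularly when few cases argue for few covariates. This stands in part. Because the endpoint also refers to protection, readers will want to know whether the association survives adjustment for the stratum. Reporting both estimates meets either reading.

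Finally, SAP 5.1.2.4 and 5.7 say that the formulation is not being taken further, that cases will be limited, and that efficacy analyses may not be done at the final analysis. That lowers the stakes but does not cancel the analysis. Efficacy endpoints remain in the 6-month interim (Protocol 9.5, SAP 5.4).

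**Conclusion.** The omission is real. Age group is missing from the only specification of the correlate models, although it is the randomization stratum and the SAP uses it in its other regressions. The titre odds ratio may be confounded by age if age affects both titre and case risk. Neither the size nor the direction can be fixed from the documents.

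Under the assumptions above, a true odds ratio of 1 per log10 would be reported as about 0.76 to 1.25, and the range narrows if titres are more spread out. A reader might conclude that a correlate would be invented or hidden. The documents do not support that: with the limited number of cases expected, the illustrated shift lies inside the interval around the estimate, and no decision rule in the plan uses this coefficient.

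Priority is low to moderate. The analysis is secondary and descriptive and might not be performed at the final analysis.

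**What to change.** In SAP 5.1.2.4, prespecify age group (18-49, 50 and over) as a covariate in the correlate-of-risk models, including the versions with titre in quantile categories. Report the titre odds ratio with its interval both with and without age group. State that a penalized (for example Firth) or exact fit will be used if cases are sparse or separation occurs; it is not needed as the default for every model.

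The cost is one degree of freedom with few cases, which may widen the interval slightly, and one extra column in the table. Age group is already collected, so no change to study conduct is needed.

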- Cohort 1: approximately 365 days duration total
- Cohort 2: approximately 386 days duration total

Data Monitoring Committee: No

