9.2 Sample Size Determination

This is a first-in-human study to assess the safety profile and immune responses to different formulations of the study vaccine when compared to placebo. A total of 440 participants will be enrolled. No formal power calculation has been performed. The sample size was determined based on logistical considerations and common practices for first-in-human trials.

Vaccine arms will be aggregated to perform complementary assessments on the following main effects: age [(18-49 years [N=240], \geq 50 years [N=120]), dose (low [N=180], high [N=180]), injection schedule (1-injection [N=120], 2-injection [N=240]), adjuvant type (AS03 [N=240], AF03 [N=120]), overall adjuvant (high-dose with adjuvants [N=180], high-dose without adjuvants [N=20]), and dose-sparing adjuvant (low-dose with adjuvants [N=180], high-dose without adjuvants [N=20]).

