3.1 Trial Design

This is a Phase I/II, randomized, modified double -blind (observer-blind), first-in-human, parallel group, placebo-controlled, dose ranging, multi-center study with a Sentinel Safety Cohort and Early Safety Data Review (ESDR) to evaluate the safety and immunogenicity profile of a COVID-19 vaccine in the population of healthy seronegative adults 18 years or older in the US. Enrollment will be stratified by age: 300 participants 18-49 years of age and 140 participant aged 50 years or older. All 440 participants will be randomized to receive either 1 injection (Cohort 1) or 2 injections (Cohort 2) of the study intervention.

As a precautionary step, a Sentinel Safety Cohort of 6 participants (younger adults only) within each dosing group from Cohort 1 will be enrolled. Upon demonstration of acceptable safety demonstrated from unblinded data review by limited members of the Sponsor Study Team (Responsible Medical Officer, Biostatistician and Programmer, Pharmacovigilance Science

Expert, and Global Safety Officer), the remaining participants in Cohort 1 and all participants in Cohort 2 will be enrolled.

Participants aged 18-49 years:

will be randomized to 6 groups to receive Antigen Formulation 1 (low-dose [5 µg]) with either AF03 or AS03 adjuvant; Formulation 2 (high-dose [15 µg]) with either AF03, AS03, or no adjuvant; or placebo (Note: unadjuvanted arm included in Cohort 2 only)

N = 20 participants in each group, except for AS03-adjuvanted groups in Cohort 2 with 60 participants in each group

Participants aged \geq 50 years:

will be randomized to 5 groups to receive Antigen Formulation 1 (low-dose [5 µg]) or Formulation 2 (high-dose [15 µg]) each with either AF03 or AS03; or placebo

N = 10 participants in each group, except for AS03-adjuvanted groups in Cohort 2 with 30 participants in each group

[figure not shown]
A subset of 87 participants in Cohort 2 (60 participants 18-49 years of age [18 per group in AS03-adjuvanted vaccines; 6 per group in all other study groups] and 27 participants \geq 50 years of age [9 per group in AS03-adjuvanted groups; 3 per group in all other study groups, with the exception of the unadjuvanted group for which there will be no older adults]), will be randomly assigned to a cellular-mediated immune (CMI) subset

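### VE counts cases only up to an outside COVID-19 vaccine but divides by numbers of subjects, so unequal time at risk between vaccine and placebo would bias it in either direction

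*SAP*

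**What the plan says.** SAP 5.1.2.4 sets the numerator: "Efficacy analyses will be performed on COVID-19 cases collected before receiving an authorized/approved COVID-19 vaccine". It then defines VE as 1 - (Cv/Nv)/(Cp/Np), where Nv and Np "are the numbers of subjects in the vaccine and placebo groups, respectively".

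The interval comes from q = Cv/(Cv + Cp). An exact Clopper-Pearson interval for q is converted through VE = 1 - (Np/Nv) x q/(1 - q). The Bayesian step puts a beta(1,1) prior on q and uses the same conversion, with VE thresholds from 0% to 30% and a 95% probability criterion.

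The first three vaccine pools are "pooled all vaccine arms; 2) pooled low-dose and high-dose with adjuvants arms; 3) pooled high dose with adjuvants arms". The fourth is "pooled cohort 1 vaccine arms and cohort 2 vaccine arms". No placebo comparator is named for any pool, and no start day is given for counting cases.

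SAP 5.2.5 runs efficacy on the FAS and on the per-protocol set for immunogenicity (PPAS-IAS). SAP 5.4 plans efficacy at the 6-month interim. SAP 5.1.2.4 and 5.7 warn that the efficacy analyses may be dropped at the final analysis.

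**The concern.** The numerator is cut at the outside vaccine and the denominator is not. A participant who takes an authorised vaccine early contributes little time in which a case could count, but still counts as one whole subject. The formula recovers VE only if mean time at risk per subject is the same in the vaccine and placebo groups. Neither document gives a person-time, time-to-event or cohort-stratified version.

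The SAP applies the censoring idea elsewhere: section 4.4.1.1.5 treats the outside-vaccine date as a censoring date for days of solicited reaction. Uptake is also expected to matter, since SAP 5.1.2.4 foresees few cases before an outside vaccine.

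At stake are the VE point estimate, its interval and the probability set against the 95% criterion. All three would absorb any difference in exit timing, and nothing in the planned efficacy output would show it.

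**Working it through.** **Inputs from the documents.** SAP 3.1 gives arm sizes for ages 18-49 ("N = 20 participants in each group, except for AS03-adjuvanted groups in Cohort 2 with 60 participants in each group") and for 50 and over ("N = 10 participants in each group, except for AS03-adjuvanted groups in Cohort 2 with 30 participants in each group"). The unadjuvanted arm is in Cohort 2, younger adults only. Planned follow-up in the Protocol Synopsis is about 365 days for Cohort 1 and 386 for Cohort 2. Active surveillance ends at D181 or D202 (Protocol 8.2.2.2), that is, after 180 or 201 days.

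**Reproducing the plan's pools.**
- Cohort 1 vaccine: 4 x 20 + 4 x 10 = 120.
- Cohort 2 adjuvanted: (20 + 60 + 20 + 60) + (10 + 30 + 10 + 30) = 240. Both figures match Protocol 9.2.
- Adding the 20 unadjuvanted gives 260 in Cohort 2 and 380 vaccinees in all.
- Placebo: 30 + 30 = 60. The total is 440, as planned.
- Cohort 2 share: 260/380 = 68% of all vaccinees, 240/360 = 67% of the pool of all adjuvanted arms, and 30/60 = 50% of placebo.

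**Bias formula.** With a constant infection rate and rare cases, the expected SAP estimate is 1 - (1 - true VE) x r, where r = mean time at risk in vaccine / mean time at risk in placebo.

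**Outside-vaccine timing that differs by arm (retention assumed; the documents give none).**

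| Retained person-time, vaccine v placebo | r | True VE 0% | True VE 30% | True VE 50% |
|---|---|---|---|---|
| 80% v 70% | 1.143 | -14% | 20% | 43% |
| 70% v 80% | 0.875 | 13% | 39% | 56% |
| equal | 1.000 | 0% | 30% | 50% |

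Over a wider assumed range with true VE 0%, r = 0.80, 0.90, 1.10 and 1.25 give +20%, +10%, -10% and -25%.

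**Planned cohort mix alone, true VE 0%.**
- Full follow-up: vaccine (120 x 365 + 260 x 386)/380 = 379.4 days; placebo (30 x 365 + 30 x 386)/60 = 375.5 days; r = 1.010; VE = -1.0%.
- To D181/D202: 194.4 v 190.5 days; r = 1.020; VE = -2.0%.
- The adjuvanted pools give -0.9% and -1.8%.

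**Outside-vaccine timing that differs by cohort (assumed means of 120 and 200 days), equal by arm within cohort.** If Cohort 1 stops earlier, vaccine is (120 x 120 + 260 x 200)/380 = 174.7 days and placebo 160 days, so r = 1.092 and VE = -9.2%. If Cohort 2 stops earlier, VE = +9.2%.

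**One cohort's vaccine arms against both placebo arms pooled.** Planned follow-up alone gives r = 365/375.5 = 0.972 for Cohort 1 (VE +2.8%) and 386/375.5 = 1.028 for Cohort 2 (VE -2.8%). To D181/D202 the shifts are +5.5% and -5.5%.

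**Effect on the interval and the Bayesian step (case counts assumed, 380 v 60 subjects).** The posterior for q is beta(Cv + 1, Cp + 1). VE exceeds VE0 when q < (1 - VE0)/[(1 - VE0) + Np/Nv]. The person-time version replaces Np/Nv by (Np/Nv)/r.
- 15 v 3 cases: subjects give VE 21% (95% CI -325% to 78%); person-time with r = 0.80 gives 1% (-432% to 72%).
- 12 v 5 cases: the probability that VE exceeds 0 is 0.972 with subjects and 0.938 with person-time at r = 0.80, on opposite sides of 95%. At r = 0.875 it is 0.955, still above.

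**The case against.** The bias is conditional. Participants, investigators and outcome assessors are blinded to vaccine group, and unblinding before an outside vaccine is not required, so exit timing may well be similar by arm. That stands: the documents show no difference. Nor do they exclude one. The injection schedule is open, Protocol 2.3 expects more injection site reactions with adjuvant while placebo is saline, and SAP 5.4 accepts that published interim results may reach participants and sites.

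Three stronger readings are tempting, and the documents do not support them.
- A reader might infer that uneven cohort pooling manufactures efficacy. By the planned schedule the vaccine pools have slightly more time than placebo, so the shift is small and against the vaccine.
- A reader might infer that placebo recipients guess their arm and leave sooner. No passage says so.
- A reader might take Nv and Np to be everyone enrolled. They are counts in the FAS or PPAS-IAS. The PPAS excludes recipients of Category 2 therapy, which includes other vaccines (Protocol 6.5, SAP 5.2.3). Outside-vaccine recipients may therefore leave both numerator and denominator in PPAS-IAS, and the mismatch is clear only in the FAS.

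The practical weight is limited. VE is secondary and descriptive, planned placebo is 60, the intervals are very wide, and final efficacy may be dropped. This lowers the priority but leaves the formula wrong for the 6-month interim.

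**Conclusion.** The point holds as a conditional one. In the FAS, the SAP's VE, exact interval and Bayesian probability are free of this bias only if mean time at risk before an outside vaccine is equal in vaccine and placebo. If it is not, the error follows r directly: -14% or +13% at a true VE of 0% for an assumed 80% v 70% retention and its reverse, and nothing when retention is equal. The planned cohort mix alone accounts for about -1% to -2%. It matters more only if outside-vaccine timing also differs by cohort, or if a single cohort is set against both placebo arms.

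These sizes assume a constant infection rate and rare cases, and the retention figures are illustrations. Neither the existence nor the direction of a real imbalance can be read from the documents.

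**What to change.** 1. Replace Nv and Np by person-time at risk in the VE formula, the q-to-VE conversion and the Bayesian step. Count from first injection to the earliest of case, outside vaccine or end of follow-up. A single exact interval with a person-time offset then works as before.
2. For serological infection, which is seen only at scheduled samples (Protocol Table 8.1), end person-time at the first positive sample or at the last sample before the outside vaccine.
3. State whether the fourth pool is one group or two, and name the placebo comparator for every pool. Where VE is given by cohort, compare each cohort's vaccine arms with that cohort's own placebo.
4. If pooled VE is stratified by cohort, use a method built for strata, for example an exact stratified analysis or Poisson regression with a person-time offset. One q with one Clopper-Pearson interval and one beta posterior does not carry across strata.
5. Report outside-vaccine uptake and mean time at risk by arm and cohort.

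The cost is some extra derivation and programming and an SAP update. COVID-19 vaccinations are already recorded in the CRF under the schedules of activities, so no new data are needed. Two limits remain: person-time corrects fully only if the infection rate is roughly constant and exit is unrelated to infection risk, and it spans active surveillance and the later passive-only period. Reporting VE to D181/D202 separately would deal with the second.
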